#### 7.3.4 Investigator Notification

The CTU should be notified within 24 hours of the investigator becoming aware of an event that requires expedited reporting (i.e. any expected or unexpected Serious Transfusion-related Adverse Reaction, major bleeding episodes or SAEs). Investigators should notify the CTU of all such events occurring during the study period.

The SAE/Transfusion reaction or major bleed form must be completed by the Investigator (the consultant named on the delegation of responsibilities log who is responsible for the patient's care). In the absence of the Investigator, the form should be completed and signed by a member of the site trial team and faxed or emailed. The responsible Investigator should subsequently check, annotate and sign the form and re-fax/email to the CTU as soon as possible. The initial report must be followed by detailed written reports as appropriate.

The Investigator must record all expected SAEs that occur during the study period on the SAE listing form, but are not required to immediately notify them to the CTU.

The investigator must follow-up all reported SAEs until resolution or the event is considered stable.

Investigator must supply the CTU, REC and relevant NHS Trust R&D with any supplementary information they request.

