#### 7.2 Adverse Events that do not Require Reporting

Any event that does not meet the definition of serious does not need to be recorded for this trial.

Participants in this study have a bone marrow failure disorder and some may have comorbidities. Some of these patients will be expected to develop SAEs during the course of the study, many of which will be unrelated to trial interventions. These events are not required to be reported as SAEs, however we will be capturing the listed events below in the CRF. Similarly disease progression, or death as a result of disease progression, are not considered to be SAEs and should be reported on the end of study form.

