#### **Expected SAEs:**

- Admission to the intensive care unit
- Severe sepsis
- Major organ dysfunction (single or multi-organ)

\*\*The term 'life-threatening' in the definition of 'serious' refers to an event in which the patient was at risk of death at the time of the event; it does not refer to an event which hypothetically might have caused death if it were more severe.

\*\*\*Hospitalisation is defined as an inpatient admission, regardless of length of stay, even if the hospitalisation is a precautionary measure for continued observation. Hospitalisations for a pre-existing condition (including elective procedures that have not worsened) do not constitute an SAE.

- Transient ischaemic attack, Thromboembolic and ischaemic events (myocardial infarction, stroke, pulmonary embolus, DVT)
- Acute transfusion reactions to red cell blood components including indicators of transfusion associated circulatory overload (TACO) and transfusion related acute lung injury (TRALI) i.e. Congestive cardiac failure, Pulmonary oedema (definitions as described in SHOT)

If an adverse event meets the definition of an SAE and it is considered unexpected it must be recorded on an SAE form and be faxed / e-mailed to the CTU within 24 hours of the site becoming aware of it.

As this is a trial of a blood component, it is not appropriate to assess causality of any SAE and there is no requirement on the form to do so. However, any red cell transfusion reactions that occur must have their imputability assessed using the definitions in Table 7b below. There are five categories: N/A = Not assessable 0 = Excluded or unlikely, 1 = Possible, 2 = Likely (probable), and 3 = Certain. The severity of any red cell transfusion reaction will also be graded using SHOT criteria as 1 = mild, 2 = moderate or 3 = severe Two clinicians sitting on the TMG will independently review this data at the end of the study.

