#### 7.3.1 Investigator Assessment of AEs

When an AE or AR occurs, the investigator responsible for the care of the patient must first assess whether or not the event is serious using the definitions in Table 7a: definitions. If the event is serious and is on the list of expected events in section 7.1, then the details must be recorded on the AE form. If the event does not fit any of the exempted categories, it must be recorded on an SAE form and faxed to the CTU within 24 hours of becoming aware of it.

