#### 7.3.3 Expectedness of Transfusion Reactions

If the event is a Serious Transfusion-Related Adverse Reaction, the Investigator must assess the expectedness of the event. Please refer to section 7.3.3.1 for a list of expected red cell transfusion reactions. It is highly unlikely that an unexpected Serious Adverse Transfusion Reaction will occur, but the possibility must not be excluded. If a Serious Transfusion Related Adverse Reaction is assessed as being unexpected, the PI must notify the CTU.

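### Section 7 gives contradictory instructions on whether, how and how fast an expected serious red cell transfusion reaction is notified to the CTU

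*Protocol*

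**What the plan says.** The instructions are spread over section 7 of the Protocol and a box in the front matter.

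- **Section 7.2** says of events unrelated to the intervention and foreseeable in this population: "These events are not required to be reported as SAEs, however we will be capturing the listed events below in the CRF". The list that follows, headed as expected SAEs, includes "Acute transfusion reactions to red cell blood components including indicators of transfusion associated circulatory overload (TACO) and transfusion related acute lung injury (TRALI". An SAE form within 24 hours is asked for when a serious event is considered unexpected.
- **Section 7.3.1** routes a serious event to the AE form if it is "on the list of expected events in section 7.1". Section 7.1 contains definitions and no such list.
- **Section 7.3.3** says that if a serious reaction "is assessed as being unexpected, the PI must notify the CTU". It gives no time limit and regards such an event as very improbable. The expected reactions in 7.3.3.1 include anaphylaxis, haemolysis, TRALI, TACO, bacterial contamination and transfusion of the wrong component.
- **Section 7.3.4, first paragraph**, requires notification within 24 hours of "any expected or unexpected Serious Transfusion-related Adverse Reaction, major bleeding episodes or SAEs".
- **Section 7.3.4, third paragraph**, says that investigators record expected SAEs on the SAE listing form "but are not required to immediately notify them to the CTU".
- **The notification box after section 7.5** allows five working days for the SAE, Major Bleed or Transfusion Reaction form and sets no condition on expectedness.
- **The SAE reporting box in the front matter** gives one working day for a reportable SAE.

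**The concern.** These are the operative instructions that a site follows when a serious reaction occurs, so this is not a matter for the statistical analysis plan. The trial compares two levels of red cell exposure, and serious transfusion reactions are a direct harm of that exposure.

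Oversight while the trial runs depends on reports reaching the CTU. Under section 7.4 the Chief Investigator reviews the transfusion reaction and major bleed reports that the CTU has received, and the DMC is sent SAE reports. The only review of transfusion reaction data named in 7.2 is by two clinicians from the Trial Management Group at the end of the study.

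If sites read different paragraphs, the speed of notification will depend on the site as well as on the event. A difference between sites in the reports seen during the trial could then reflect reading habits and not harm.

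**Working it through.** No arithmetic applies. The check is to take one event, a serious TACO within 24 hours of a red cell transfusion, and follow it through each instruction. TACO is on the expected lists in both 7.2 and 7.3.3.1.

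| Place in the Protocol | Notify the CTU? | Form | Time limit |
|---|---|---|---|
| 7.2 | Not as an SAE | CRF | None stated |
| 7.3.1 | Not stated | AE form | None stated |
| 7.3.3 | Duty stated for unexpected reactions; this one is expected | None named | None stated |
| 7.3.4, first paragraph | Yes, whatever the expectedness | SAE/Transfusion reaction or major bleed form (second paragraph) | 24 hours |
| 7.3.4, third paragraph | Not immediately | SAE listing form | None stated |
| Box after 7.5 | Yes, no expectedness condition | SAE, Major Bleed or Transfusion Reaction form | Five working days |
| Front-matter box | Only if it counts as a reportable SAE | SAE form | One working day |

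Four things follow.

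1. **Section 7.3.4 contradicts itself.** The 7.2 list of expected SAEs contains "Acute transfusion reactions to red cell blood components". An expected serious acute reaction is therefore also an expected SAE. The first paragraph of 7.3.4 requires notification within 24 hours, and the third says immediate notification is not required. The third paragraph contains no exception for transfusion reactions.
2. **Sections 7.2 and 7.3.3 point away from the first paragraph of 7.3.4.** A site that works from 7.2 and 7.3.3 would conclude that expectedness decides notification. The expected list in 7.3.3.1 is broad and 7.3.3 thinks unexpected serious reactions very improbable, so that site would send few or no expedited reports. A site that works from the first paragraph of 7.3.4 would send one for every serious reaction.
3. **The time limits differ.** They are 24 hours (7.3.4), one working day (front matter) and five working days (box after 7.5). The first and last apply to the same transfusion reaction report. Even a site that decides to notify cannot tell from the document how quickly.
4. **The cross-reference in 7.3.1 is wrong.** It sends the reader to 7.1 for a list that is in 7.2.

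The scope has a limit. The 7.2 exemption names acute reactions, and 7.3.3.1 defines acute as up to 24 hours after transfusion. A serious delayed reaction is not clearly exempt, so the conflict is established for expected acute reactions.

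**The case against.** The strongest reply is that the Protocol runs transfusion reactions and major bleeds on a track separate from SAEs. Section 7.1 says transfusion-related events are reported separately, 7.4 sends transfusion reaction reports to the Chief Investigator and SAE reports to the DMC, and the box after 7.5 names separate forms. On that view the 7.2 statement that "These events are not required to be reported as SAEs" removes only the SAE route and leaves the Transfusion Reaction form in place. Section 7.3.3 does not say that only unexpected reactions are notified, and its expectedness step matches the reporting of unexpected reactions to the ethics committee in 7.4. The section actually headed for investigator notification covers expected and unexpected reactions alike.

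This is a fair reading and probably close to the intention. It does not remove the contradiction inside 7.3.4, because acute reactions stand on the list that the third paragraph releases from immediate notification. Nor does it explain five working days against 24 hours.

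The objection to the form names also has some force. CRF may be a generic term, and nothing shows that the AE form and the SAE listing form are not CRF pages. That part may be no more than inconsistent naming.

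A reader might go further and infer that nearly all serious reactions could go unreported during the trial, or that the Chief Investigator would have nothing to review. The Protocol does not support that:

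- On the most lenient reading the events are still recorded on the CRF, AE or listing form. Section 6.2.1 sends CRF copies to the CTU, and 8.2 has data managers review what arrives.
- Transfusion reactions are a clinical outcome in 9.2.3.
- Section 7.5 keeps SHOT/SABRE reporting in force.
- The box after 7.5 asks for a Transfusion Reaction form whatever the expectedness.

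These routes do not replace prompt notification. Section 6.2.1 sets no deadline for CRF copies, and the Protocol does not say that SHOT/SABRE reports reach the CTU or the DMC.

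**Conclusion.** The contradiction stands on the text. For an expected serious acute transfusion reaction, the Protocol both requires and waives prompt notification to the CTU, and it offers three different time limits. What is at risk is the timing and uniformity of notification, and through it of review by the Chief Investigator and DMC. The existence of the record is not at risk.

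The size cannot be quantified. The Protocol gives no expected number of serious reactions and no indication of which paragraph sites would follow, so a percentage of missed notifications would be invented. The conclusion assumes only that different sites may reasonably follow different paragraphs. It does not touch the primary outcomes or the sample size.

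**What to change.** Reconcile 7.2, 7.3.1, 7.3.3, 7.3.4, the box after 7.5 and the front-matter box to one notification rule, one named form and one time limit for serious transfusion reactions. The choice of rule is the sponsor's. One solution that fits the Protocol's own text is:

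- State in 7.2 and 7.3.3 that serious transfusion reactions are notified under 7.3.4 whatever their expectedness, and that expectedness decides only the reporting to the ethics committee under 7.4.
- In the third paragraph of 7.3.4, except serious transfusion reactions and major bleeds from the release from immediate notification.
- Correct the cross-reference in 7.3.1 from 7.1 to 7.2, and use one form name throughout.
- Align the time limits in 7.3.4 and the two boxes.

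The cost is a wording amendment to section 7 and the front matter, plus a few more expedited forms, which the first paragraph of 7.3.4 already asks for.

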#### 7.4 Sponsor's Responsibilities

The CTU (on behalf of the Sponsor) will forward all red cell transfusion reactions and major bleed reports received to the Chief Investigator (or a medically qualified delegate) for review.

The CTU will review all SAE reports and forward to the Data Monitoring Monitoring Committee (DMC) for review, as often as instructed by them, and also provide them as listings for review at DMC meetings. These will be copied to the Chief Investigator for review.

Agree the planned content of both blinded and unblinded DMC reports with DMC members prior to the inclusion of the first trial participant.

The CTU is undertaking the duties of trial sponsor and is responsible for the reporting of any unexpected Serious Transfusion-Related Adverse red cell reactions to the research ethics committee (REC), should any occur, and for preparing annual safety reports to the REC.

#### 7.5 Statutory Reporting

Hospital staff remain responsible for reporting all transfusion-related adverse events to SHOT/SABRE according to standard procedures, as required under the regulations of the EU Blood Directive. Staffs at the institution are also responsible for notifying their local R&D department of SAEs (as per the institutions standard local procedure).

# NOTIFICATION OF SAEs/ RED CELL TRANSFUSION REACTIONS

Within five working days of becoming aware of an event , please fax a completed SAE , Major Bleed or Transfusion Reaction form to the NHSBT/ Clinical Trials Unit on:

[contact]

Or email information to :(Serious Adverse [contact])

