## SAE REPORTING

Within one working day of becoming aware of a reportable SAE, please fax a completed SAE Form to the NHSBT CTU on

[name]

Or email information to :(Serious\_Adverse\[contact])

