#### 7.3.2 Investigator Assessment of Transfusion Reactions

As this is a trial of a blood component, it is not appropriate to assess causality of any SAEs and there is no requirement on the form to do so. However, any transfusion reactions that occur must have their imputability assessed using the definitions in Table 7b. There are 5 categories: unrelated, unlikely, possible, probable and definitely related.

Table 7b: Definitions of Imputability

Relationship	Description	
Unrelated	There is no evidence of any causal relationship	
Unlikely	There is little evidence to suggest there is a causal relationship (e.g. the event	
	did not occur within a reasonable time after administration of the trial transfusion).	
	There is another reasonable explanation for the event (e.g. the patient's clinical	
	condition, other concomitant treatment).	
Possible	There is some evidence to suggest a causal relationship (e.g. because the event	
	occurs within a reasonable time after administration of the trial transfusion).	
	However, the influence of other factors may have contributed to the event (e.g.	
	the patient's clinical condition, other concomitant treatments).	
Probable	The evidence is clearly in favor of attributing the adverse reaction to the blood or	
	blood component.	

Definitely	There is conclusive evidence beyond reasonable doubt attributing the adverse
	reaction to the blood or blood component.

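### The protocol gives sites conflicting deadlines for the SAE form (24 hours, one working day, five working days) and leaves unsettled whether expected serious transfusion reactions are expedited

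*Protocol*

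**What the plan says.** **Deadlines.** The SAE reporting box in the front matter reads "Within one working day of becoming aware of a reportable SAE". Section 7.2 says of an SAE judged unexpected that "it must be recorded on an SAE form and be faxed / e-mailed to the CTU within 24 hours of the site becoming aware of it". Section 7.3.1 repeats the 24-hour limit for the SAE form when a serious event falls outside the exempted categories. Section 7.3.4 reads "The CTU should be notified within 24 hours of the investigator becoming aware of an event that requires expedited reporting", and counts serious transfusion reactions, major bleeding episodes and SAEs as such events. The notification box after section 7.5 reads "Within five working days of becoming aware of an event", and applies this to the completed SAE, major bleed or transfusion reaction form.

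**Expected serious transfusion reactions.** Section 7.3.4 expedites "any expected or unexpected Serious Transfusion-related Adverse Reaction". Later in the same section, sites must enter expected SAEs on a listing form "but are not required to immediately notify them to the CTU". The expected-SAE list in section 7.2 includes "Acute transfusion reactions to red cell blood components", with indicators of circulatory overload and acute lung injury, and 7.2 also says that such events need not be reported as SAEs. Section 7.3.3 states a duty to notify the CTU only when the serious reaction is judged unexpected.

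**Imputability.** Section 7.2 grades transfusion reactions as not assessable or 0 to 3 and points to Table 7b for the definitions. Section 7.3.2, which contains that table, says "There are 5 categories: unrelated, unlikely, possible, probable and definitely related".

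**The concern.** These are binding instructions to sites, and they cannot all be followed as written. The closing box carries the fax and e-mail details, so staff are likely to act on it. A site that uses its full allowance for an SAE form complies with the box and breaches sections 7.2 and 7.3.1. Sites could follow different pages in good faith, and a monitor would have no single standard to hold them to.

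The second conflict is not a rare case. Section 7.3.3.1 classes anaphylactic, haemolytic, circulatory-overload, lung-injury and contamination reactions as expected, and section 7.3.3 regards an unexpected serious reaction as highly unlikely. Whether expected reactions are expedited therefore decides the handling of nearly every serious transfusion reaction in the trial. Transfusion reactions are also a listed clinical outcome in section 9.2.3.

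**Working it through.** The protocol gives no statistical figure to reproduce here. The check sets the passages side by side and converts the limits to elapsed time.

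**1. What each place requires**

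| Place | Limit | What must arrive | Events |
|---|---|---|---|
| Front-matter box | one working day | SAE form | reportable SAEs |
| 7.2 | 24 hours | SAE form | unexpected SAEs |
| 7.3.1 | 24 hours | SAE form | serious events not exempted |
| 7.3.4 | 24 hours | notification | serious transfusion reactions, major bleeds, SAEs |
| Closing box | five working days | completed form | SAE, major bleed, transfusion reaction |

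**2. Elapsed time.** Assume a Monday-to-Friday week, no public holidays, and counting from the day after awareness.

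- One working day: awareness Monday to Thursday gives 1 calendar day; Friday to Monday gives 3; Saturday gives 2; Sunday gives 1.
- Five working days: awareness on any weekday gives 5 + 2 = 7 calendar days; Saturday to the following Friday gives 6; Sunday to Friday gives 5.
- Against 24 hours (1 day), the closing box therefore allows 5/1 = 5 to 7/1 = 7 times as long.

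One working day and 24 hours nearly coincide in midweek and part mainly over weekends. Five working days agrees with neither.

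**3. Can the closing box be reconciled with the rest?**

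- *As the limit for non-expedited events only.* The box speaks of an event without qualification, and 7.3.4 sends expected SAEs to a separate listing form, not to the forms named in the box.
- *As the limit for a full form after a 24-hour first notice.* For major bleed and transfusion reaction forms this is possible, since 7.3.4 requires notice within 24 hours and foresees fuller written reports later. The box does not say so. For the SAE form the reading fails, because 7.2 and 7.3.1 put the form itself under the 24-hour limit.

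**4. Expected serious transfusion reactions.** Take a serious circulatory-overload reaction. By the definition of expedited events in 7.3.4, the CTU hears of it within 24 hours. By the list in 7.2 it is an expected SAE, so by the later sentence in 7.3.4 it goes on the listing form without immediate notice. Section 7.3.3 supports the second route, since it imposes notification only for unexpected reactions. Section 7.3.1 adds a smaller slip: it places the expected list in section 7.1, though the list is in 7.2, and sends such events to an AE form where 7.3.4 names an SAE listing form.

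**5. Imputability scales**

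| Section 7.2 | Table 7b |
|---|---|
| Not assessable | no counterpart |
| 0, excluded or unlikely | Unrelated; Unlikely |
| 1, possible | Possible |
| 2, likely (probable) | Probable |
| 3, certain | Definitely |

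The upper three grades correspond. Two Table 7b grades collapse into grade 0, and one grade in 7.2 has no match.

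**The case against.** The best defence is that the 24-hour rule is not one rule stated three times. Sections 7.2 and 7.3.1 concern the SAE form for particular SAEs; 7.3.4 concerns notice, covers more events, and expects detailed reports to follow. Prompt notice with a completed form some days later would be a workable scheme. This stands in part: for major bleed and transfusion reaction forms the conflict is one of unclear wording. It does not rescue the SAE form.

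On expected reactions, 7.3.4 names serious transfusion reactions separately from SAEs, so the specific rule may be meant to override the general exemption. That reading is natural, but no sentence says so, and 7.2 and 7.3.3 point the other way.

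Three stronger inferences are not supported:

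- *The Data Monitoring Committee would see events late.* Section 7.4 sends it SAE reports as often as it asks and as listings at meetings, so a delay of some days need not change what it sees.
- *Imputability data could not be combined.* Collapsing two categories aligns the scales except for the not-assessable grade, and two clinicians on the Trial Management Group review these data at study end.
- *The trial's results are at risk.* The primary outcomes (9.2.1) and the feasibility criterion (9.4) rest on haemoglobin values. Listed expected events are still captured on the CRF (7.2), bleeding is scored daily (6.3), and statutory reporting by hospital staff runs separately (7.5).

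**Conclusion.** The point holds as an internal contradiction that should be fixed. For the SAE form, the closing box allows about five to seven calendar days where 7.2 and 7.3.1 allow 24 hours, on the assumptions of a Monday-to-Friday week, no public holidays, and counting from the day after awareness. Seven days is roughly the upper end of that range, not a minimum. The one-working-day box is a lesser discrepancy that shows mainly over weekends. Whether expected serious transfusion reactions are expedited is unresolved in the current text. The mismatch in imputability scales is real but secondary.

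What is affected is how promptly and uniformly serious events reach the CTU and, through it, the Chief Investigator. The documents do not establish an effect on the primary outcomes or on what the Data Monitoring Committee sees, and they do not by themselves show which deadline the sponsor intended.

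**What to change.** The sponsor should:

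1. Reconcile the front-matter box, sections 7.2, 7.3.1 and 7.3.4, and the closing box to one stated deadline. The body of section 7 uses 24 hours throughout, but the choice is the sponsor's. If a completed form may follow later than the first notice, the closing box should say so and name the forms to which this applies.
2. State once whether expected serious transfusion reactions are expedited, and align 7.2, 7.3.3 and 7.3.4 with that statement. Correct the cross-reference and the form name in 7.3.1 at the same time.
3. Use one imputability scale in 7.2, 7.3.2 and Table 7b. If reactions have already been graded, record how the two scales were mapped and what was done with the not-assessable grade.

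The cost is a wording amendment and a note to sites. No new data are needed.

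### The protocol sets conflicting deadlines for sending safety forms to the CTU: 24 hours, one working day and five working days for the SAE form, and 24-hour notice against a five-working-day form for serious transfusion reactions and major bleeds

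*Protocol*

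**What the plan says.** Five places in the protocol set a time limit for reporting to the CTU.

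- **Front-matter SAE reporting box:** "Within one working day of becoming aware of a reportable SAE, please fax a completed SAE Form to the NHSBT CTU on" the number that follows. It names the SAE form only.
- **Section 7.2, under the list of expected SAEs:** the rule for a serious event that is not counted as expected is "it must be recorded on an SAE form and be faxed / e-mailed to the CTU within 24 hours of the site becoming aware of it".
- **Section 7.3.1:** for a serious event outside the exempted categories, "it must be recorded on an SAE form and faxed to the CTU within 24 hours of becoming aware of it".
- **Section 7.3.4:** "The CTU should be notified within 24 hours of the investigator becoming aware of an event that requires expedited reporting". The events covered are serious transfusion reactions, expected or not, major bleeds and SAEs. The next paragraph names the SAE, transfusion reaction and major bleed forms. A later paragraph has expected SAEs entered on a listing form, with no immediate notification.
- **Unnumbered notification box after section 7.5:** "Within five working days of becoming aware of an event", sites are to fax a completed SAE, Major Bleed or Transfusion Reaction form.

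**The concern.** The closing box carries the fax and email details and is headed as the instruction for notifying SAEs and red cell transfusion reactions, yet its limit is much longer than the limits in the numbered sections before it. A site can follow the box to the letter and breach sections 7.2 and 7.3.1.

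Under section 7.4 the CTU forwards transfusion reactions and major bleeds to the Chief Investigator, passes SAE reports to the DMC, and reports unexpected serious transfusion reactions to the REC. Each step starts from receipt at the CTU, so late receipt can delay each one. Timeliness also has no single standard against which to judge a site.

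**Working it through.** The protocol derives no figure from these deadlines, so the check is a comparison of the texts by form, followed by a count of days.

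**Which limits apply to which form**

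| Form or event | Front-matter box | Sections 7.2 and 7.3.1 | Section 7.3.4 | Closing box |
|---|---|---|---|---|
| SAE form | 1 working day | 24 hours, for the form itself (unexpected SAEs) | 24 hours, notification | 5 working days |
| Serious transfusion reaction | not named | no separate limit | 24 hours, notification | 5 working days (Transfusion Reaction form) |
| Major bleed | not named | not named | 24 hours, notification | 5 working days (Major Bleed form) |

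The SAE form therefore has three limits. The other two forms have a 24-hour notification rule set against a five-working-day rule for the form.

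**Can the texts be read together?**

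1. *24-hour notice first, form within five working days.* This is arguable for bleeds and reactions, because section 7.3.4 times the notification and gives no explicit time for the form. It fails for the SAE form, since sections 7.2 and 7.3.1 put the form itself under the 24-hour limit.
2. *Five working days for expected SAEs only.* Section 7.3.4 sends those to a separate listing form. The closing box names the SAE form.
3. *Five working days for follow-up or non-serious reports.* The box contains no such restriction.

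**Size of the gap**

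Assumptions: Monday to Friday working week, no public holidays, day of awareness counted as day 0, and Monday counted as the first working day after weekend awareness. Lateness = calendar days to the end of the five-working-day window − the comparison limit in calendar days (24 hours = 1 day).

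| Aware on | 1 working day ends after | 5 working days end after | Past 24 hours | Past 1 working day |
|---|---|---|---|---|
| Mon–Thu | 1 day | 7 days | 7 − 1 = 6 | 7 − 1 = 6 |
| Fri | 3 days | 7 days | 7 − 1 = 6 | 7 − 3 = 4 |
| Sat | 2 days | 6 days | 6 − 1 = 5 | 6 − 2 = 4 |
| Sun | 1 day | 5 days | 5 − 1 = 4 | 5 − 1 = 4 |

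A form sent at the end of the window leaves the site 5 to 7 calendar days after awareness, 4 to 6 days past the 24-hour limit. The 24-hour and one-working-day limits coincide except for awareness on Friday (3 − 1 = 2 days apart) and Saturday (2 − 1 = 1 day apart). The material conflict is five working days against the other two.

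**A related conflict inside section 7.3.4**

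It asks for 24-hour notification of SAEs without qualification and of expected serious transfusion reactions, then exempts expected SAEs from immediate notification. Acute transfusion reactions, including TACO and TRALI, are on section 7.2's list of expected SAEs, so a serious reaction of that kind falls under both rules.

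**The case against.** The best case for the protocol is that all these limits are upper bounds. A form sent within 24 hours normally satisfies every one of them, so nothing impossible is asked. The front-matter box, which also carries contact details, says one working day, and section 2.3 provides for staff training in the procedures, so sites need not fall back on the longest limit. Section 7.4 lets the DMC decide how often it sees SAE reports, so form receipt does not alone set the timing of its review. SHOT/SABRE reporting runs separately (section 7.5), and treating physicians know the allocation and may depart from it (sections 5.5 and 5.6), so bedside care does not wait for the CTU. These points stand. They limit the consequence but do not remove the contradiction over the latest permitted time.

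A reader might infer more than the text supports:

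- *That every form carries three deadlines.* The front-matter box names only the SAE form.
- *That reports would arrive a week late.* Seven days is the longest time since awareness in the count above. Lateness against 24 hours is at most 6 days, and only if the whole window is used.
- *That a week's delay is one sixth of the time on each strategy (7/42).* The synopsis counts day +42 from the last chemotherapy dose, and section 5.7.2 lets a cycle end when the next one starts, so 42 days is not the length of exposure.
- *That timeliness cannot be monitored at all.* Section 8.3 leaves monitoring to a separate plan. What is missing is an agreed limit to monitor against.
- *That 24 hours should apply to every form.* Section 7.3.4 expedites serious transfusion reactions only. A blanket rule would add a requirement for non-serious reactions that the protocol does not state.

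**Conclusion.** The contradiction is real and stands in the current text. Removed contact details do not explain it, and no passage says which limit governs. It is firmest for the SAE form, where 24 hours, one working day and five working days all apply to the completed form. For serious transfusion reactions and major bleeds it is 24-hour notification against five working days for the form, and it is softer because notification and form could be read as separate steps.

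Its size is 4 to 6 days past the 24-hour limit, on the stated working-day assumptions and for a site that uses the full window. Public holidays, or a different convention for weekend awareness, would lengthen it. How many sites would follow the closing box cannot be known from the protocol. The consequence is possible delay to safety oversight; sample size, power and analysis are not affected. Because it concerns a mandatory safety instruction and costs little to correct, it should be corrected.

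**What to change.** Reconcile the front-matter box, sections 7.2, 7.3.1 and 7.3.4, and the closing box to one stated deadline per event type and form, confirmed by the sponsor. For reference, 24 hours is what the body sections already state for unexpected SAEs (7.2 and 7.3.1) and for serious transfusion reactions and major bleeds (7.3.4). Say in each case whether the limit applies to first notification or to the completed form.

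Remove the five-working-day limit, or relabel it so that it covers only what it was meant for, such as follow-up information or non-serious reactions.

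In the same edit, state whether expected SAEs, and expected serious transfusion reactions in particular, need 24-hour notification or only an entry on the listing form.

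The cost is a wording amendment and a note to sites. No data collection, sample size or analysis changes.
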